#### **4.11. Ethical Considerations**

The study will be hospital-based descriptive study regarding the clinical effectiveness and safety of amphotericin B with flucytosine-fluconazole combination therapy for treatment of HIV-associated cryptococcal meningitis. In this study, all patients according to selection criteria admitted to inpatient departments of SHW, SHM and SHT will be included. The participants eligible to the selection criteria will be invited to voluntary participation in the study and then explained in details about the study by the investigator with the information sheet of informed consent form (Part-I).

Only after they have understood the nature of study, objectives, methodology, procedure and duration, they can voluntarily take part in the study or they have right to refuse or withdraw at any time from the study without penalty of loss of benefit to which he or she would otherwise be entitled. If they agree, the written informed consent will be obtained by using informed consent form (Part-II) from all participants or from parents/relatives/next of kin if the patient could not provide the consent.

[figure not shown]
The study will be done under the supervision of a physician. The study will collect data under routine management. No new drugs will be administered and no treatment will be restricted for the purpose of thesis. The participants will be closely monitored throughout the research process. If any adverse reactions occur, the researcher will immediately inform to the physician and urgent treatment will be given and the necessary actions will be taken according to the standard treatment procedure.

The investigator will strictly maintain the rules of privacy and confidentiality. The name of patients will not be mentioned in this study. Only coded system will be used and research information will be kept by a password-protected file in the investigator's personal computer. All the personal information of the subject in Pro forma will be destroyed and the personal information in the investigator's personal computer will be deleted after the study period. The presentation on research data will be used in medical workshop, seminars and conference and the data will also be published for the academic purposes- only in thesis, papers and medical journals if necessary.

This study will follow the research guidelines of University of Pharmacy and laid out in the booklet - Manual for protocol and dissertation/ Thesis writing (2020). The research protocol will be submitted and approved by the Ethic Review Committee (ERC) of University of Pharmacy.

It is the duty of the investigator to perform the research study according to the objectives, methodology and procedures approved by ERC of University of Pharmacy.

#### 4.12. Algorithm

## 5. DUMMY TABLES

Table 4. Number of Cryptococcal meningitis in patients with HIV infection enrolled from individual specialist hospital

Hospital	Number (N)	Percentage (%)
Specialist hospital Waibargi		
Specialist hospital Mingalardon		
Specialist hospital Thakeyta		
Total		

Table 5. Distribution of age among study group of Cryptococcal meningitis in patients with HIV infection

Age (completed years)	Amphotericin B, Flucytosine plus Fluconazole group	
	Number	Percentage
≤20		
21-40		
>40		
Total		

Table 6. Distribution of gender among study group of Cryptococcal meningitis in patients with HIV infection

Gender	Amphotericin B, Flucytosine plus Fluconazole group	
	Number	Percentage
Male		
Female		
Total		

Table 7. Frequency distribution of headache among study group by Numerical rating Scale at day-1, day-7 and day-14

Days	Headache	Amphotericin B, Flucytosine plus Fluconazole group	
		Number	Percentage
day-1	No pain		
	Mild		
	Moderate		
	Severe		
	Intolerable		
Day-7	No pain		
	Mild		
	Moderate		
	Severe		
	Intolerable		
Day-14	No pain		
	Mild		
	Moderate		
	Severe		
	Intolerable		

Table 8. Clinical effectiveness of study group by assessing presence of headache, fever, convulsion, abnormal mental status and death at day-1, day-7 and day-14

Clinical parameters	Amphotericin B, Flucytosine plus Fluconazole group					
	Day 1		Day 7		Day 14	
	N	%	N	%	N	%
Headache						
Fever						
Convulsion						
Abnormal mental status						
Death						

Table 9. Laboratory-defined adverse events of amphotericin B, flucytosine and fluconazole at baseline and day-7 and day-14 by DAIDS grading

Days	DAIDS Grading	Hematological parameters & Biochemical parameters								Total
		Anaemia N (%)	Neutropenia N (%)	Thrombocytopenia N (%)	Elevated ALT level N (%)	Elevated AST level N (%)	Hypokalemia N (%)	Hyper creatinemia N (%)		
Baseline	Grade 1									
	Grade 2									
	Grade 3									
	Grade 4									
Day-7	Grade 1									
	Grade 2									
	Grade 3									
	Grade 4									
Day-14	Grade 1									
	Grade 2									
	Grade 3									
	Grade 4									

Table 10. Proportion of patients with grade 3 and 4 adverse events of hematological parameters at baseline, day-7 and day-14

	Grade 3 and 4 adverse events	Baseline		Day -7		Day -14	
		N	%	N	%	N	%
Amphotericin B, Flucytosine plus Fluconazole group	Anaemia						
	Neutropenia						
	Thrombocytopenia						
Total							

Table 11. Proportion of patients who has bone marrow suppression at baseline, day-7 and day-14

Bone marrow suppression	Baseline		Day -7		Day -14	
	N	%	N	%	N	%
Amphotericin B, Flucytosine plus Fluconazole group						
Total						

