#### **4.8. Materials and Methods**

After getting approval from medical superintendent, patients with HIV-associated cryptococcal meningitis admitted to inpatient departments of SHW, SHM and SHT will be studied. They will be given IV infusion of amphotericin B (1 mg/kg/day) and oral flucytosine (100 mg/kg) for one week followed by oral fluconazole (1200 mg/day) for one week according to the hospital standard treatment guideline chosen by the physician depends on patient's clinical condition. Before giving treatment, informed consent will be obtained.

All patients meeting the inclusion criteria will be studied under the supervision of experienced physicians. Baseline data for assessing clinical effectiveness such as fever, convulsion and abnormal mental status and for safety such as hematological and biochemical parameters (hemoglobin, neutrophil, platelet, ALT, AST, serum creatinine and serum potassium level) will be noted from medical charts. Hematological and biochemical parameters will be graded according to DAIDS grading. Assessment of headache and its severity will be done by numerical rating scale under the supervision of physician.

Seven days and fourteen days after treatment, clinical effectiveness parameters such as headache, fever, convulsion, abnormal mental status and death will be reassessed. Clinical safety concerning hematological and biochemical parameters like hemoglobin, neutrophil, platelet, ALT, AST, serum creatinine and serum potassium level will also be reassessed and graded according to DAIDS grading by reviewing from patient's medical charts at seven and fourteen days. With regard to severity of headache, it will be documented by using numerical rating scale at weekly intervals for two weeks. Clinical effectiveness parameters (headache, fever, convulsion, abnormal mental status and death) and hematological and biochemical parameters will be described. The results will be documented for data analysis.

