#### **4.9. Data Management and Analysis**

Data will be collected by using pre-constructed pro forma. Following data collection and prior to data entry, all data will be carefully screened for accuracy.

Data entry will be done by using Microsoft Excel 2019. The data will be statistically analyzed by using computerized statistical software SPSS (Statistical Package for Social Science Version 21).

Data summarization for description will be done by showing frequency distribution tables and appropriate graphs. The parameters for clinical effectiveness and laboratory-defined adverse event gradings will be described by number, percentage in treatment group.

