##### **(3) Clinical Effectiveness**

Clinical effectiveness will be assessed by using these parameters such as headache, fever, convulsion, abnormal mental status and death.

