#### I. Personal Identification

IPD Registration No. -----

Name -----

Age -----

Gender       Male       Female

Date of Admission -----

Occupation -----

Address -----

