## VI. Assessment of Headache (Headache Severity by Numerical rating scale)

Days	Numerical rating Scale				
	No pain 0	Mild 1-3	Moderate 4-6	Severe 7-9	Intolerable 10
Day 1					
Day 7					
Day 14					

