## VII. Assessment of Fever

Days	Temperature (morning)	
	Present	Absent
Day 1		
Day 7		
Day 14		

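### Death is a named effectiveness parameter, but the data form has no place to record it and Table 8 has no rule for patients who died, so deaths can read as symptom resolution

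*Combined protocol and SAP*

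**What the plan says.** Section 4.10(3) makes death one of five parameters: "Clinical effectiveness will be assessed by using these parameters such as headache, fever, convulsion, abnormal mental status and death". Section 4.8 states that, seven and fourteen days after treatment, "clinical effectiveness parameters such as headache, fever, convulsion, abnormal mental status and death will be reassessed". Table 8 in Section 5 ("Clinical effectiveness of study group by assessing presence of headache, fever, convulsion, abnormal mental status and death at day-1, day-7 and day-14") gives each of the five a row, with N and % at each day.

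Section 4.9 names the collection instrument, "Data will be collected by using pre-constructed pro forma", and the analysis: "The parameters for clinical effectiveness and laboratory-defined adverse event gradings will be described by number, percentage in treatment group".

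The pro forma in Annex 1 runs without a break from item I to item X. Item I records the "Date of Admission". Items VI to IX (for example "VII. Assessment of Fever") give headache, fever, convulsion and abnormal mental status a grid for days 1, 7 and 14. Headache has five severity categories; the other three have present or absent. No item records death, date of death or vital status, and no grid can show that a patient had died or was not assessed.

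Neither Section 4.9 nor Tables 7 and 8 give a denominator for day 7 or day 14. Section 4.12 has a heading but no text in the copy reviewed, so nothing is inferred from it.

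**The concern.** There are two linked gaps. First, a named outcome has a results row but no collection field. A blank in a symptom grid could mean dead, withdrawn or missed.

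Second, a patient can leave a symptom's present count in Table 8 by recovering or by dying, and the plan does not separate the two. Objective 2 is met by describing these parameters at days 1, 7 and 14. The study is descriptive, with one group and no planned test, so the change across Table 8's columns is the effectiveness result. If deaths contribute to that change unseen, the table can show improvement where there was none.

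**Working it through.** **The plan's own figure.** Section 4.7.1 uses n = z²p(1−p)/d². Safety: 1.96² × 0.83 × 0.17 / 0.14² = 27.66. Effectiveness: 1.96² × 0.8 × 0.2 / 0.15² = 27.32. The stated 27 is the truncated value. It is not in question here and serves only as the denominator for illustration.

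**Assumed deaths.** Section 2.1.13 cites 2-week mortality of 9/63 = 14.3% (exact 95% CI 6.7% to 25.4%). Applied to 27 patients this is 3.9 deaths (1.8 to 6.9), so about 4, range 2 to 7. This is an assumption; the plan gives no expected mortality for its own patients.

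**General rule.** Let a of N patients have the symptom at day 1, D die, and s of the dead have had it. Nobody improves and there is no new onset.

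- All treated: (a − s)/N. Each death of a symptomatic patient removes 1/27 = 3.7 points.
- Survivors: (a − s)/(N − D). This is below a/N when s/D > a/N and above it when s/D < a/N. What matters is how common the symptom was among the dead compared with the whole group at day 1, not whether most of the dead had it.
 - Convulsion 5/27 = 18.5%, 1 of 4 dead affected (25%): 4/23 = 17.4%, a fall, although 3 of the 4 lacked it.
 - Fever 23/27 = 85.2%, 3 of 4 dead affected (75%): 20/23 = 87.0%, a rise, although 3 of the 4 had it.

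**Headache, nobody improves.** Take 27/27 at day 1 (Section 2.1.5 reports 100% in Myanmar studies).

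| Deaths | All treated | Survivors |
|---|---|---|
| 2 | 25/27 = 92.6% | 25/25 = 100% |
| 4 | 23/27 = 85.2% | 23/23 = 100% |
| 7 | 20/27 = 74.1% | 20/20 = 100% |

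**Headache near the plan's expectation.** Take p = 0.8 improvement from Section 4.7.1, read here as headache-free. With 4 deaths, 0.2 × 23 = 4.6, so about 5 survivors still have headache: 5/27 = 18.5% or 5/23 = 21.7%, a difference of 3.2 points. Shown in full, the 27 are 5 present, 18 absent (18/27 = 66.7%) and 4 died.

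**Abnormal mental status, nobody improves.** 46.7% in Section 2.1.5 gives about 13/27 = 48.1% at day 1. With 4 deaths:

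| Dead who had it | All treated | Survivors |
|---|---|---|
| 4 | 9/27 = 33.3% | 9/23 = 39.1% |
| 2 | 11/27 = 40.7% | 11/23 = 47.8% |
| 0 | 13/27 = 48.1% | 13/23 = 56.5% |

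**What the Death row can and cannot resolve.** Suppose Table 8 shows 13 at day 1, 9 at day 14 and 4 deaths. With no new onset, recoveries = 13 − s − 9 = 4 − s, anywhere from 0 to 4. Alive and symptom-free is 27 − 4 − 9 = 14/27 in every one of these cases, so that summary alone does not separate recovery from death either. Day-1 status must be linked to day-14 outcome.

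**The case against.** The documents do not fix the denominator. The Section 4.9 phrase may only echo the single column heading of the dummy tables, and Section 4.12 is empty in the copy reviewed. Deaths stand beside the symptom rows in Table 8. Where a count is above zero, N and % together reveal the denominator. Table 7 lists a no-pain category, so its counts sum to the patients scored and a shortfall would show unless deaths were entered as no pain. Charts are reviewed at both days, Section 4.8 requires death to be reassessed, and Section 4.11 promises close monitoring. The no-improvement case runs against the plan's own 0.8. The 9/63 comes from a paragraph that runs several studies together, so its regimen is unclear. The study is descriptive and no decision rule depends on these percentages.

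Much of this stands, and it limits the size of the problem. It does not remove it. The Death row says how many died, not which symptoms they had, and the form has no field to supply even that row. Symptoms and laboratory values also come from routine care, yet they have form fields. A survivors-only denominator is not a cure, as the mental-status table shows.

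It is tempting to set the 14.8-point fall with 4 deaths (100% to 85.2%) against the planned precision of 0.15. These are different quantities: 0.15 is the precision for the proportion whose headache improves, not for a change in symptom prevalence.

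**Conclusion.** The point holds and should be fixed. Followed as written, the form leaves a named effectiveness outcome uncollected, and the visible text does not say how patients who died enter Table 8's symptom rows.

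A reader might infer that Table 8 will show deaths as improvement, or that deaths will be lost. The documents support neither. The first depends on a denominator that the plan leaves open, although all treated patients is the plain reading of Section 4.9. The second is unlikely because the charts are reviewed.

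The size depends on deaths and on true improvement. Under the all-treated reading, with 2 to 7 deaths in 27, universal headache at day 1 and no improvement, the apparent fall is 7.4 to 25.9 points; this is the upper end. Near 80% improvement with 4 deaths, the choice of denominator moves the figure by about 3 points.

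**What to change.** 1. Add vital status at day 7 and day 14, with date of death, to the pro forma. Add separate died and not-assessed options to the symptom grids.
2. State that Table 8's Death row is cumulative, out of all enrolled.
3. For each symptom at day 7 and day 14, report present, absent, died and not assessed as four separate categories that sum to all enrolled. In Table 7, add died and not assessed as two separate rows. Alive and symptom-free out of all enrolled can then be read directly, with living but unassessed patients (including withdrawals under Section 4.6.3) kept visible.
4. For each symptom, cross-tabulate day-1 status (present, absent) against day-14 status (present, absent, died, not assessed), so that recoveries can be told from deaths.

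Percentages among assessed survivors may be added if labelled as such.

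Cost: one form item, completed at chart reviews already planned, plus revised grids and dummy tables. No extra patients are needed. Some percentages may look less favourable.

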#### **3.2. Objectives**

1. To find out the back-ground characteristics of patients with HIV-associated cryptococcal meningitis
2. To describe the clinical effectiveness of amphotericin B with flucytosine-fluconazole combination therapy by assessing clinical parameters at day 1, day 7 and day 14
3. To determine the severity of headache before and after treatment by numerical rating scale
4. To describe the clinical safety of amphotericin B with flucytosine-fluconazole combination therapy by assessing hematological and biochemical parameters by DAIDS grading at baseline, day 7 and day 14

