###### **(ii) Fever**

It is defined as rise in body temperature above 37 °C (98.6 °F) in the morning.

(iii) Convulsion

It is defined as a medical condition where body muscles contract and relax rapidly and repeatedly, resulting in uncontrolled actions of the body.

(iv) Abnormal mental status

It is defined as patients is somnolent, lethargy, disoriented and disruptions in perception and behavior.

(4) Clinical safety

Clinical safety will be assessed by laboratory defined adverse events. Adverse event is defined as any untoward medical occurrence in a subject to whom a medicinal product has been administered including occurrences which are not necessarily caused by or related to that product (Division of AIDS, 2017). Laboratory parameters (hematological and biochemical parameters) such as HGB, NEUT, PLT, ALT, AST, serum creatinine, serum potassium level will be graded according to DAIDS grading in appendix 3. Bone marrow suppression is defined as Grade 3 and 4 adverse events in one or more of anaemia, neutropenia and thrombocytopenia.

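### Tables 9–11 label baseline laboratory grades as adverse events and count each visit separately, so in general they do not show how many patients newly reached, worsened to, or at any time after baseline had grade 3/4

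*Combined protocol and SAP*

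**What the plan says.** Objective 4 (section 3.2), which covers all three visits, is "To describe the clinical safety of amphotericin B with flucytosine-fluconazole combination therapy by assessing hematological and biochemical parameters by DAIDS grading". Section 4.9 says that "laboratory-defined adverse event gradings will be described by number, percentage in treatment group". It plans no other summary of the laboratory data.

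Three dummy tables in section 5 carry the laboratory safety results, each with its own counts for the three visits:

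- Table 9: "Laboratory-defined adverse events of amphotericin B, flucytosine and fluconazole at baseline and day-7 and day-14 by DAIDS grading"
- Table 10: "Proportion of patients with grade 3 and 4 adverse events of hematological parameters at baseline, day-7 and day-14"
- Table 11: "Proportion of patients who has bone marrow suppression at baseline, day-7 and day-14"

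For section 4.10, item (4) Clinical safety, an adverse event means "any untoward medical occurrence in a subject to whom a medicinal product has been administered". Causation is not required, since the definition extends to events described by the words "including occurrences which are not necessarily caused by or related to that product". The same item adds: "Bone marrow suppression is defined as Grade 3 and 4 adverse events in one or more of anaemia, neutropenia and thrombocytopenia".

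Section 4.7.1 sizes the safety part on the proportion without grade III/IV anaemia after treatment (p = 0.83, absolute precision 0.14) and gives no time point. Section X of the pro forma (Annex 1) records each patient's haemoglobin, neutrophils, platelets, ALT, AST, creatinine and potassium at all three visits.

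**The concern.** There are two faults.

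The first is labelling. The definition in section 4.10 does not require that the drug caused the event, but it does require that a product has been given. Section 4.8 separates baseline from the reassessments seven and fourteen days after treatment, so baseline is naturally read as pre-treatment. Table 9 nevertheless titles baseline grades as adverse events of the three drugs, and Table 10 has a baseline column under a grade 3 and 4 adverse-event heading. Table 11 does the same indirectly, because bone marrow suppression is itself defined through adverse events.

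The second is that visits are not linked within a patient. The study has one group and no comparator, so the patient's own baseline is the only internal reference. Pregnancy is the only listed exclusion, so cytopenia before treatment is possible. Two later counts of the same size may come from the same patients or from different ones, and may include patients who were already grade 3/4 on admission. Per-visit counts do not tell these cases apart. The reader then cannot say how many patients got worse on treatment, or how many were affected at any time after it began.

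**Working it through.** **1. The plan's own figure.** The formula in section 4.7.1 is n = z²p(1−p)/d².

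- Safety: 1.96² × 0.83 × 0.17 / 0.14² = 27.66
- Effectiveness: 1.96² × 0.80 × 0.20 / 0.15² = 27.32

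The plan states 27 for both. Rounding up would give 28, but one patient does not affect this point, so 27 is used below.

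**2. What each table can identify.** Table 9 gives counts by grade and visit, with no row for patients without an abnormality. Table 10 gives grade 3/4 counts by visit for the three blood-cell lineages. Table 11 gives the composite by visit. None crosses one visit with another. In the DAIDS table (Annex 3), only creatinine has grades relative to the participant's own baseline. Those are alternatives to the upper-limit-of-normal criterion, and creatinine does not appear in Tables 10 or 11.

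**3. Illustration.** The visit counts are assumptions; the documents give none. Take N = 27, everyone measured, and grade 3 anaemia in b = 3 at baseline, 5 at day 7 and 5 at day 14. A new case is a patient below grade 3 at baseline and at grade 3 at day 7 or day 14.

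Suppose k of the 3 baseline cases persist at both visits and the other 3 − k are below grade 3 at both. Each later visit then has 5 − k affected patients who were not baseline cases. With complete overlap between visits, new cases number 5 − k. With no overlap, they number 2(5 − k). Patients affected at either visit are the new cases plus k.

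| Baseline cases persisting (k) | New cases | Affected at either visit |
|---|---|---|
| 3 | 2 to 4 (7.4% to 14.8%) | 5 to 7 (18.5% to 25.9%) |
| 2 | 3 to 6 | 5 to 8 |
| 1 | 4 to 8 | 5 to 9 |
| 0 | 5 to 10 | 5 to 10 |

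Enumerating every patient-level pattern with these counts, including baseline cases that persist at only one visit, gives overall ranges of 2 to 10 new cases (7.4% to 37.0%) and 5 to 10 affected at either visit (18.5% to 37.0%). The upper end needs all baseline cases to resolve and no overlap between day 7 and day 14.

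**4. Other assumed counts.** Counts of 5/5/5 fit 0 to 10 new cases. Counts of 0/5/5 still fit 5 to 10. Counts of 0/5/0 give exactly 5. The tables therefore identify the answer in special cases but not in general.

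**5. Link to the sample-size quantity.** With 3/5/5, Table 10 implies 22/27 (81.5%) free of grade 3/4 anaemia at day 14. Freedom at both visits is 20 to 22 of 27 (74.1% to 81.5%) if all baseline cases persist, and 17 to 22 of 27 (63.0% to 81.5%) over all patterns. Section 4.7.1 does not say which is meant.

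**The case against.** The strongest reply is that the tables do what objective 4 asks. It calls for a description by DAIDS grade at three visits, in a study that section 4.1 calls descriptive. Days 7 and 14 match the ends of the two treatment phases in section 4.8, so a per-visit display is a reasoned choice. Baseline columns are useful context, and a column marked baseline is unlikely to be taken for a drug effect. All of this stands. It supports keeping the per-visit columns, but it does not make the baseline wording agree with section 4.10 or supply the linked result.

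A reader might infer that the tables carry no denominators. That goes too far. Tables 8 to 11 pair counts with percentages, so a non-zero cell lets the reader recover the denominator used. Table 7 lists every headache category including none, so it sums to the number assessed for headache. Tables 10 and 11 also have a total row, whose meaning is undefined. The fair criticism is that the numbers measured for laboratory values are not labelled.

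A reader might also infer that the ambiguity exceeds the planned precision of 14 points, since 81.5 − 63.0 = 18.5. The documents do not support that. The counts are invented, and 18.5 is reached only at the extreme bound. If all baseline cases persist, the gap is 81.5 − 74.1 = 7.4 points. The comparison is also ill-matched, because d is a sampling half-width and the gap is a difference between two definitions. If section 4.7.1 means day 14, Table 10 already gives the matching result as a complement.

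Nor do the documents show that cytopenia at baseline will be common. Under sections 4.5 and 4.8, only patients given this regimen are studied, and the physician chooses it in light of the patient's condition.

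**Conclusion.** The point holds as a reporting weakness that should be corrected. The baseline label conflicts with the protocol's own definition of an adverse event. The planned tables and section 4.9 also leave new, worsened and either-visit grade 3/4 unidentified in general. Both conclusions rest on the text alone.

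The size depends on assumed counts. In the 3/5/5 example with complete data, the same table entries fit a twofold range of new cases (2 to 4) if all baseline cases persist, and 2 to 10 as a logical range that should not be read as likely.

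Complete data is itself optimistic. Section 2.1.13 cites 9 of 63 patients dead at two weeks in one study. At that rate, 27 × 9/63 = 3.9, or about 4 patients, which is as many as the new cases at issue. Denominators therefore need to be defined.

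A reader might conclude that the study misses its safety objective or cannot describe safety. It does neither: objective 4 is met as per-visit prevalence, the linked data will exist, and the sample size is unaffected.

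**What to change.** Use the values already on the pro forma:

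1. Label the baseline rows and columns of Tables 9–11 *baseline abnormality*.
2. Keep the per-visit columns and label the number measured at each visit.
3. For each of the seven parameters, tabulate baseline grade by worst grade at day 7 or day 14.
4. For each parameter and for bone marrow suppression, report two proportions with 95% confidence intervals:
   - (a) Any grade 3/4 at day 7 or day 14. Denominator: patients with at least one post-baseline value.
   - (b) Grade 3/4 at day 7 or day 14 that is at least one grade worse than the patient's own baseline. Denominator: patients with a baseline value below grade 4 and at least one post-baseline value. For bone marrow suppression, the criterion is met in at least one lineage, and the denominator is patients with at least one lineage evaluable in this way.
5. State separately how many patients died or were unmeasured before each visit, and how many were already grade 4 at baseline and so could not worsen.
6. State which time point the anaemia proportion in section 4.7.1 refers to, and report the matching result.

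No new visits, tests or data are needed. The cost is slightly more analysis: seven shift tables, some of them sparse at n = 27, and 16 proportions (two for each of seven parameters and one composite).
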